3.9.1 Procedures for discontinuation of a subject from investigational product

At any time, patients are free to discontinue investigational product or withdraw from the study (i.e., investigational product and assessments – see Section 3.10), without prejudice to further treatment. A patient that decides to discontinue investigational product will always be asked about the reason(s) and the presence of any adverse events. If possible, they will be seen and assessed by an Investigator(s). Adverse events will be followed up; and all study drugs should be returned by the patient.

If a patient is withdrawn from study, see Section 3.10.

3.10 Criteria for withdrawal

The term withdrawal from the study refers to discontinuation from both study medication and study assessments.

Specific reasons for withdrawal from study are:

- Voluntary discontinuation by the patient who is at any time free to discontinue his/her participation in the study, without prejudice to further treatment (see Section 3.10.2)
- Severe non-compliance to protocol as judged by the Investigator and/or Sponsor
- Patient lost to follow-up
- Death

The date and reason for patient withdrawal must be recorded on the appropriate electronic Case Report Form (eCRF). Every attempt should be made to contact any patient considered lost to follow-up.

It is understood by all concerned that an excessive rate of withdrawals can render the study uninterpretable; therefore, unnecessary withdrawal of patients should be avoided.

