3.9 Discontinuation of investigational product

Patients may be discontinued from investigational product (IP) in the following situations:

- Patient decision. The patient is at any time free to discontinue treatment, without prejudice to further treatment.
- Adverse Event

Clinical Study Protocol Drug Substance ZS Study Code **D9480C00001** Version **6.0** Date **19** August 2020

- Severe non-compliance with the study protocol
- Risk to patient as judged by investigator
- Pregnancy
- Require treatment with medications prohibited or contraindicated for use due to safety concerns with ZS
- Start dialysis while in the study
- Patient unblinded due to emergency
- Patients who change or switch RAAS inhibitor and/or diuretic dose during the study
- Patient develops severe hypokalemia (i-STAT potassium values <3.0 mmol/L) at any time during the study or has i-STAT level > 6.2 mmol/L during the 28-day randomized treatment study phase (confirmed by taking a second potassium measurement after a 10 ± 2-minute interval, and both i-STAT values meet the study drug discontinuation rule). Patients discontinuing due to this criterion must immediately receive appropriate medical treatment to manage their hypo- or hyperkalemia.
- Patient has a clinically significant cardiac arrhythmia (see below) at any time in the 28day randomized treatment study phase, the patient should immediately receive appropriate medical treatment and be discontinued from study drug. Any of the following cardiac events will result in immediate discontinuation from the study drug (independent of whether it is in the open-label initial phase or the 28-day randomized treatment study phase):
 - Serious cardiac arrhythmias (ventricular tachycardia or ventricular fibrillation, new atrial fibrillation or atrial flutter, new paroxysmal supraventricular tachycardia [other than sinus tachycardia], new 2nd or 3rd degree AV block or significant bradycardia [HR < 40 bpm])
 - Acute heart failure
 - Significant increase in PR interval (> 250 msec in the absence of pre-existing atrioventricular block), widening of the QRS complex (>140 msec in the absence of pre-existing bundle branch block) or new onset peaked T-wave

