 - An absolute QTc >550msec, or an increase in QTc interval > 60msec from baseline to more than 500msec. All patients meeting the QTc>500ms criterion should immediately have potassium assessed by i-STAT and central lab, if not already done within 1 hour of the collection of the ECG. The QTc(f) algorithm (QT interval corrected by the Fridericia method) is recommended.

Patients who discontinue from study medication during the 28-day randomized treatment study phase but agree to remain in the study should continue to follow protocol-specified procedures and assessments except for dispensing of study medication for the study.

Any patient who is discontinued from the study treatment during open-label initiation phase will return to the clinic 7 (\pm 1) days after the last IP administration for an EOS visit. Note: Discontinuation of investigational product does not necessarily imply discontinuation of follow-up or termination of all study participation.

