8.3 Definitions of analysis sets

Unless otherwise specified, all efficacy analyses will be performed using the full analysis set (FAS), which is based on the Intent-to-Treat (ITT) principle. That is, patients allocated to a treatment group will be followed up, assessed, and analysed as members of that group irrespective of their compliance with the planned course of treatment.

The FAS includes all randomized patients. Patients without any post randomization data will not be used in any of the analyses, but will be accounted for in summary statistics tables. Explicit definitions are presented in Section 8.3.1 below.

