4.2.1.1 Definition

Several intercurrent events of concern have been identified in this setting, namely the use of disallowed medications, changes in treatment, including discontinuations, and death. For the main analysis of the primary endpoint a treatment policy approach to all the identified intercurrent events will be used (except for death, for which such an approach is not applicable).

However, a supplementary analysis aimed at evaluating the impact of disallowed medication use is included. In this analysis, the S-K (or i-STAT, if applicable) measurements obtained while a subject was receiving disallowed medication are excluded, reflecting a hypothetical scenario where disallowed medication is not available to subjects (i.e. a "hypothetical strategy" type of approach, see ICH E9 (R1) 2017 p. 18).

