	phase, th	e patient should immediately receive appropriate			
	medical t	treatment and be discontinued from study drug. Any			
	of the fol	lowing cardiac events will result in immediate			
	discontin	uation from the study drug (independent of whether			
	it is in th	e open-label initial phase or the 28-day randomized			
	treatment	t study phase):			
	3.11.1	- Serious cardiac arrhythmias (ventricular		- EDC Automatic Check	DM:
		tachycardia or ventricular fibrillation, new atrial		- Source Data review	AE:DOSIDISC
		fibrillation or atrial flutter, new paroxysmal			
		supraventricular tachycardia [other than sinus	CSD v6 0		
		tachycardia], new 2nd or 3rd degree AV block or	(10 Aug 2020)		
		significant bradycardia [$HR < 40$ bpm])	(19-Aug-2020)		
3.11	3.11.2	- Acute heart failure		- B&I Programming -	DM: EG2, EG3:
				Source Data review	DOSDISC
	3.11.3	- Significant increase in PR interval (> 250 msec		- EDC Automatic Check -	DM: EG,
		in the absence of pre-existing atrioventricular		Source Data review	EG2,EG3:
		block), widening of the QRS complex (>140 msec			DOSDISC
		in the absence of pre-existing bundle branch block)			
		or new onset peaked T-wave.			
	3.11.4	- An absolute $QTc > 550msec$, or an increase in		- EDC Automatic Check	DM: AE:
		QTc interval > 60msec from baseline to more than		for QTcF only	DOSDISC
		500msec. All patients meeting the QTc>500ms		- B&I Programming -	
		criterion should immediately have potassium		Source Data review	
		assessed by i-STAT and central lab, if not already			
		done within 1 hour of the collection of the ECG.			
		The QTc(f) algorithm (QT interval corrected by the			

	Fridericia method) is recommended.			
4	Discontinuation Criteria for overall study withdrawal met b	out patient not wit	hdrawn from study	
4.1	Voluntary discontinuation by the patient	CSP v6.0 (19-Aug-2020)	- Source Data review	
4.2	Severe non-compliance to protocol as judged by the Investigator and/or Sponsor	CSP v6.0 (19-Aug-2020)	- Source Data review	
5	Investigational Product (IP) Deviation			
5.1	Participant received incorrect IP (corporate IPD):Subject received incorrect IP to that to which they were randomised.	CSP v6.0 (19-Aug-2020)	- Source Data review	
5.2	Subjects who were randomised but did not receive IP	CSP v6.0 (19-Aug-2020)	- B&I Programming - Source Data review	DS: DS1: IE1; EX1: DOSDISC

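### Severe non-compliance may end all S-K follow-up under Protocol 3.10 and SAP IPD 4.2, which conflicts with a treatment-policy primary analysis; the effect is probably small, but the rules need reconciling

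*Protocol*

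**What the plan says.** **Protocol 3.10** fixes the meaning of withdrawal: "The term withdrawal from the study refers to discontinuation from both study medication and study assessments". Its four specific reasons are the patient's own decision, loss to follow-up, death, and "Severe non-compliance to protocol as judged by the Investigator and/or Sponsor". No threshold for severe is given. The section also warns that too many withdrawals can make the study uninterpretable and that unnecessary ones should be avoided.

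**Protocol 3.9** lists "Severe non-compliance with the study protocol" among the situations in which study drug may be discontinued. Patients who stop drug in the randomised phase but "agree to remain in the study should continue to follow protocol-specified procedures and assessments except for dispensing of study medication".

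**SAP Appendix A** has two matching entries. IPD 3.3 covers severe non-compliance where study treatment was not stopped. IPD 4.2 repeats the 3.10 wording under category 4, which covers patients who met a study-withdrawal criterion but were not withdrawn from the study.

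**Protocol 8.3** says that patients allocated to a group "will be followed up, assessed, and analysed as members of that group irrespective of their compliance"; the sentence goes on to specify compliance with the planned course of treatment. SAP 3.2.1 says the same.

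**SAP 4.2.1.1** names disallowed medication, changes in treatment including discontinuations, and death as intercurrent events. It states that "a treatment policy approach to all the identified intercurrent events will be used", death excepted. SAP 4.2.1.3 uses no multiple imputation in the main analysis, because little missing data is expected and what there is should be missing at random given the model covariates.

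**The concern.** A treatment-policy comparison needs S-K values after a patient stops taking study drug properly. Here one trigger, with no threshold and left to the investigator's or sponsor's judgement, can lead either to stopping drug with visits continued or to ending all assessments. A site that chooses the first can be recorded as having an important deviation under IPD 4.2.

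Patients who take ZS poorly are those whose S-K would be expected to drift back towards placebo level. If their assessments are ended, those values are never collected, and the estimate can move from the effect of assignment towards the effect in patients who adhere. The decision is made after randomisation. Of the four listed reasons, this is the only one imposed by the investigator or sponsor, so it is the one the plan can avoid.

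Nothing planned would show the effect. Adherence is not among the model covariates (SAP 3.3.6). The sensitivity and supplementary analyses of the primary endpoint (SAP 4.2.1.5) address i-STAT against central laboratory values and disallowed medication, not missingness from withdrawal.

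**Working it through.** **Inputs.** From Protocol 8.2: difference 0.30, SD 0.50, 100 patients per ZS arm and 50 on placebo, two-sided 5%, stated power above 90%. No allowance for dropout after randomisation is stated. The documents give no rate of severe non-compliance, so the fraction w is an assumption.

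**Step 1. The plan's own figure.**
- Standard error = 0.50 × √(1/100 + 1/50) = 0.50 × √0.03 = 0.0866.
- Noncentrality = 0.30 / 0.0866 = 3.46, with 148 degrees of freedom.
- Power = 93.1% by the noncentral t (93.4% by the normal approximation). The stated figure is reproduced.

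**Step 2. The rules side by side, for a patient judged severely non-compliant with treatment.**

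| Place | Consequence |
|---|---|
| Protocol 3.9 | Drug may be stopped; assessments continue if the patient agrees |
| Protocol 3.10 | Listed reason to end drug and assessments |
| SAP IPD 4.2 | Not withdrawing from the study is an important deviation |
| Protocol 8.3, SAP 3.2.1 | Follow up and assess irrespective of treatment compliance |
| SAP 4.2.1.1 | Treatment policy for treatment changes and discontinuations |

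The second and third rows cannot be squared with the last two.

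**Step 3. Upper bound on the shift in the primary estimate.** Assume that a fraction w of ZS patients is withdrawn before Day 8, so that they contribute no Day 8-29 values. Assume also that their S-K would have returned fully to placebo level, and that placebo withdrawals do not move the placebo mean. The treatment-policy difference is 0.30 × (1 − w). The analysis without these patients stays at 0.30, so the overstatement is 0.30 × w.

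| w | Treatment-policy difference | Overstatement (mmol/L) | Ratio |
|---|---|---|---|
| 3% | 0.291 | 0.009 | 1.03 |
| 5% | 0.285 | 0.015 | 1.05 |
| 10% | 0.270 | 0.030 | 1.11 |

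The largest shift is 0.030 / 0.0866 = 0.35 of a standard error.

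**Step 4. Power.** If a fraction w of every arm is lost and the difference stays at 0.30, power is 91.8% at w = 5% and 90.4% at w = 10%. If the patients are kept and non-compliers on ZS have no drug effect, power for the diluted difference is 90.5% and 87.2%. Retention is therefore not a way to gain power. Its purpose is to estimate the effect that the plan names.

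**Step 5. Other tests.** SAP section 2 replaced Day 29/Exit by Day 29, giving the ITT approach as the reason. The only replacement for a missing central laboratory value is an adjusted i-STAT value (SAP 3.3.5 and 4.2.3.6). A patient withdrawn earlier has neither, so is absent from the Day 29 logistic regression, which supplies tests 4 and 5. Time to hyperkalemia censors at the last S-K value (SAP 4.2.3.2), and censoring because of non-compliance may be informative. Withdrawn patients are not replaced (Protocol 3.10.2).

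**The case against.** Much of the opposing case stands, and it rules out several stronger readings.

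- *A reader might infer that the ITT sentence forbids any withdrawal for non-compliance.* It does not. It concerns compliance with the planned course of treatment, whereas 3.10 concerns non-compliance with the protocol, which includes missed visits. The conflict holds only where the non-compliance is with treatment. SAP 4.2.1.1 does not name non-compliance as an intercurrent event; it enters through changes in treatment and discontinuations.
- *A reader might infer that 3.9 and 3.10 prescribe opposite mandatory actions.* Protocol 3.9 says that drug may be stopped, and continued visits depend on the patient agreeing. Protocol 3.10 lists reasons and discourages unnecessary withdrawal. Alone, the protocol can be read as two levels of action with retention preferred. IPD 4.2 treats the criterion as one that must be acted on.
- *A reader might infer that the deviation list drives sites to end follow-up.* The documents do not show this. The list comes from a separate Non-Compliance Handling Plan and is reviewed before database lock, and deviations do not exclude patients from analysis (SAP 3.3.8). That protects values already collected, but not values never collected.
- *A reader might infer that adherent patients supply all the missing values.* A patient withdrawn after Day 8 keeps the values already observed, and under the unstructured covariance these inform that patient's later visits.
- *Little data may be recoverable.* Study drug is given in the clinic on nine days of the randomised phase (Protocol Table 2, note 4), so a patient who attends takes a fair share of doses under supervision. Some severe non-compliance will be non-attendance, where a retention rule recovers little.

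**Conclusion.** The inconsistency is established from the text. The same trigger may end drug only or end all assessments, and keeping the patient in assessments is classed as an important deviation. Where the non-compliance is with treatment, this contradicts the ITT definition and the treatment-policy strategy, and no planned analysis would reveal the effect of the lost values.

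The numerical consequence is unknown and probably small. The range of 0.009 to 0.030 mmol/L, or about 3% to 11% of the treatment-policy difference, should not be read as an expected bias. It is an upper bound that rests on an assumed w of 3% to 10%, withdrawal before Day 8, and full return to placebo level. Later withdrawal or partial adherence would make it smaller. Loss of these patients leaves power at 90.4% or more for w up to 10%, so the stated power is not materially affected. The change is worth making because the loss is avoidable and discretionary and occurs after randomisation, not because the primary conclusion is shown to be at risk.

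**What to change.** 1. In Protocol 3.10, remove severe non-compliance from the reasons for study withdrawal. Alternatively, state there that such patients stay in scheduled visits and S-K sampling unless they withdraw consent or are lost to follow-up.
2. Leave the study-drug provisions of Protocol 3.9 unchanged.
3. Delete IPD 4.2 from SAP Appendix A and from its source list in the Non-Compliance Handling Plan. Keep IPD 3.3, which already records the study-drug side.

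The patient's own right to withdraw is unaffected, and no visits or samples are added beyond those scheduled. The cost is a protocol amendment with the approvals that Protocol 10.5 requires, an edit to two further documents, and continued visit follow-up for a few poorly compliant patients. Little will be gained from those who do not attend.

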3.10.1 Screen failures

Screening failures are patients who do not fulfil the eligibility criteria for the study, and therefore must not be entered into the study, i.e., patients that are withdrawn prior to receiving open label treatment. These patients should have the reason for study withdrawal recorded as 'Eligibility criteria not fulfilled' (i.e., patient does not meet the required inclusion/exclusion criteria). This reason for study withdrawal is only valid for screen failures.

3.10.2 Withdrawal of the informed consent

Patients are free to withdraw from the study at any time (investigational product and assessments), without prejudice to further treatment.

A patient who withdraws consent will always be asked about the reason(s) and the presence of any adverse events. The Investigator will follow up AEs outside of the clinical study.

If a patient withdraws from participation in the study, then his/her enrolment/randomization code cannot be reused. Withdrawn patients will not be replaced.

3.11 Discontinuation of the study

The study may be stopped if, in the judgment of AstraZeneca, trial patients are placed at undue risk because of clinically significant findings that are assessed as causally related to study drug and are not considered to be consistent with continuation of the study.

Regardless of the reason for termination, all data available for the patient at the time of discontinuation of follow-up must be recorded in the eCRF. All reasons for discontinuation of treatment must be documented.

In terminating the study, the Sponsor will ensure that adequate consideration is given to the protection of the patients' interests.

4. STUDY PLAN AND TIMING OF PROCEDURES

Study Visit	Visit 1	Visit 2	Visit 3	Visit 4 ⁸	Rand. Visit	EOS ¹⁰	
Initial Phase Day	Pre- screen ³	Screen	Day 1 ¹⁴	Day 2 ¹⁴	Day 2 or 3 ¹⁴	Day 9 (+ 1d)	
Accepted visit window during prolonged public holidays ¹⁸						Day 4-16	
Written informed consent	Х	Х					
Eligibility criteria	Х		\mathbf{X}^{11}		Х		
Demographics	Х	Х					
Medical History			\mathbf{X}^{11}				
Physical exam including weight			X ^{11, 15}		X ¹⁵	X^{15}	
Access IVRS/IWRS		Х	Х		X^{12}		
Study drug (IP) dispensation			Х				
Study drug (IP) administration			Х	Х			
ECG			\mathbf{X}^{11}	Х	Х	Х	
Vital signs			\mathbf{X}^{11}		Х	Х	
Concomitant medications			X^{11}	Х	Х	Х	
Adverse events			X^{16}	Х	Х	Х	
Serious adverse events	X^{17}		Х	Х	Х	Х	
Potassium ^{6, 13}	X^2		X^4	X^5	X ⁹	X^9	
Clinical chemistry ^{1,6}			X ¹¹		Х	Х	
Hematology ^{1,6}			X^{11}		Х	Х	
Urinalysis ^{1,6}			X ¹¹		Х	Х	
Urine HCG			X ^{7,11}			X^7	
IP Reconciliation						Х	

Table 1Study Plan detailing the procedures: optional Pre-screening, screening and
open-label initial phase

1. Parameters to be measured are detailed in Table 3.

2. Blood potassium will be measured only by i-STAT at the Pre-screening visit (Visit 1).

3. Pre-screening visit is optional. Patients who meet all Pre-screening inclusion/exclusion criteria will be entered into the screening part of the study within 7 days.

4. Potassium will be measured twice 60 (±10) minutes apart within 1 day of first dose administration on the open-label initial phase Day 1(Visit 3) and at 1,2 and 4 hours (±15 min) after administration of the first dose of ZS. Potassium will be measured again at 90 minutes (±15 min) after taking the second dose for patients with i-STAT potassium ≥ 6.1 mmol/L or < 4.0 mmol/L4 hour after the first dose.

- 5. Potassium will be measured predose (0 hour) and 1 hour (±15 min) after the first dose on the open-label initial phase Day 2 (Visit 4). Patients achieving normokalemia (3.5 to 5.0 mmol/L, inclusive) based on the predose potassium value will skip the Visit 4 and will continue on the same day to the Randomization Visit procedures.
- 6. Serum clinical chemistry, including S-K, hematology and urinalysis will be measured fasting (nothing by mouth except water only for a minimum of 8 hours prior to collection). On the open-label initial phase Day 1(Visit 3), the Central Laboratory clinical chemistry and hematology samples will be collected at the same time as the 60 minutes i-STAT screening potassium sample.
- 7. For women of childbearing potential, urine-HCG will be measured at clinic, using the tube provided by Central Laboratory.
- 8. For patients who achieve normokalemia (3.5 to 5.0 mmol/L, inclusive) based on the predose i-STAT potassium value for open-label initial phase Day 2, will proceed to the Randomization Visit. For patients with i-STAT potassium values >5.0 mmol/L, they will continue on with the remaining procedures.
- 9. Central laboratory S-K sample collected as part of the serum clinical chemistry.
- 10. EOS in the open-label initial phase only for patients NOT entering the 28-day randomized treatment study phase, and occurs 7±1 day after the last administration of IP.
- 11. Baseline parameters should be measured/collected up to 1 day prior to administration of the 1st dose of study drug on the open-label initial phase Day 1(Visit 3).
- 12. If patient achieves normokalemia (3.5 to 5.0 mmol/L, inclusive) based on the predose potassium value of open-label initial phase Day 2 or Day 3, access IVRS/IWRS to proceed with the Randomization Visit. If the patient permanently discontinues dosing before the end of the open-label initial phase dosing period, access IVRS/IWRS to register subject as not randomized.
- 13. For diabetic patients all blood potassium samples should be collected prior to insulin administration whenever possible.
- 14. Study Day in Table 1 is for the open-label initial phase.
- 15. A complete physical examination should be performed within 1 day prior to administration the first dose of study drug on the open-label initial phase Day 1, and targeted physical examination will be conducted on the open-label initial phase Day 3 and 9 for patients not entering the 28-day randomized treatment study phase. Please refer to Section 5.2.2.
- 16. AEs will be collected after the patient has signed the main study informed consent, so during the Day 1 (Visit 3), investigator need to check if any AE happened since from main study inform consent.
- 17. Only SAEs will be collected after the patient has singed the optional Pre-screening informed consent.
- 18. The defined wider visit window can be applied, if patients are not able to strictly follow the pre-specified visit schedules, due to a prolonged public holiday.

Study Visit	Rand. Visit	Visit 6	Visit 7	Visit 8	Visit 9	Visit 10	Visit 11	Visit 12	Visit 13	Visit 14	EOS 9
28-day randomized treatment study phase Day ⁷	Day 1 ¹²	Day 2 ¹²	Day 5 ¹²	Day 8 ¹²	Day 12 ¹²	Day 15 ¹²	Day 19 ¹²	Day 22 ¹²	Day 26 ¹²	Day 29 ¹²	Day 35 ¹²
Accepted visit window during prolonged public holidays ⁸			Day 3-6	Day 7-9	Day 10-13	Day 14-17	Day 18-20	Day 21-24	Day 25-27	Day 28-31	Day 32-43
Eligibility criteria	Х										
Physical exam including weight ^{3, 13}	Х					Х				Х	Х
Access IVRS/IWRS ¹⁰	Х			Х		Х		Х			
Study drug (IP) dispensation ¹¹	Х			Х		Х		Х			
Study drug (IP) administration ⁴	Х	Х	Х	Х	Х	Х	Х	Х	Х		
ECG ³	Х			Х		Х		Х		Х	Х
Vital signs ³	Х					Х				Х	Х
Concomitant medications	Х	Х	Х	Х	Х	Х	Х	Х	Х	Х	Х
Adverse events (including SAEs)	Х	Х	Х	Х	Х	Х	Х	Х	Х	Х	Х
Potassium ⁶	X^2	Х	Х	Х	Х	X^2	Х	Х	Х	X^2	X^2
Clinical chemistry ^{1,3}	Х					Х				Х	Х
Hematology ^{1,3}	Х					Х				Х	Х
Urinalysis 1,3	Х					Х				Х	Х
Urine HCG											X^5
IP Reconciliation										Х	

Table 2Study Plan detailing the procedures: 28-day randomized treatment study phase

1. Parameters to be measured are detailed in Table 3.

2. Potassium will be measured fasting prior to the 1st daily dose as part of the clinical chemistry panel on Day 1, 15, 29, 35 in the 28-day randomized treatment study phase.

3. Physical Exam, ECG, Vital signs, weight, urinalysis, clinical chemistry including S-Aldo and P-Renin, and hematology parameters will be measured fasting (nothing by mouth except water for a minimum of 8 hours prior to potassium sample collection at the clinic); On the 28-day randomized treatment study phase Days 1,15, 29, and 35(EOS), blood sample which including S-Aldo and P-Renin test need to be collected prior to 10am after the patient has been upright for at least 2 hours and before the ECG.

4. Study drug will be administrated in the clinic on Day 1,2,5,8,12,15,19,22 and 26. If a patient develops i-STAT potassium values between 3.0 mmol/L and 3.4 mmol/L, inclusive (confirmed by taking a second potassium

measurement after a 10 ± 2 -minute interval, and both i-STAT values meet the study drug adjustment rule), dosing will be reduced from qd to every other day for the remainder of the study.

- 5. For women of Childbearing potential, using-HCG will be measured at clinic, using the tube provided by Central Laboratory.
- 6. All potassium samples are analyzed by i-STAT and by the Central Laboratory on all occasion. And haemolysed samples should not be sent to the Central Lab for potassium, the sample should be re-drawn to obtain a sample showing no haemolysis. For diabetic patients all blood potassium samples should be collected prior to insulin administration whenever possible.
- 7. If a scheduled clinic visit falls on a weekend or short public holiday during the 28-day randomized treatment study phase, the scheduled visit may take place either 1 day early or 1 day late (i.e., within±24 hours of the scheduled day) for the 28-day randomized treatment study phase Days 5, 8, 12, 15, 19, 22, 26 and 35, up to 2 days late for the 28-day randomized treatment study phase Day 2 or 2 days early for Day 29. If the Day 29 visit is conducted early, the patient must take IP through Day 28 per protocol.
- 8. The defined wider visit window can be applied, if patients, are not able to strictly follow the pre-specified visit schedules, due to a prolonged public holiday. If the wider visit windows are applied for a particular visit, it is important that visits before and after such a visit also follows the wider visit windows. This will only apply during prolonged public holidays. Patients are expected to follow the pre-specified visit schedule once the prolonged holiday period is over.
- 9. EOS occurs 7 ± 1 day after the last administration of IP.
- 10. Access IVRS/IWRS on visit indicated or if patient permanently discontinues dosing before the end of the 28day randomized treatment study phase.
- 11. Due to a public holiday, patients may visit the clinic up to two days after the pre-specified visit schedules, the site investigator can access the IVRS/IWRS in an earlier visit; and the system will assign the patient a new 28-day randomized treatment study phase IP kit containing an additional 7-day supply of IP.
- 12. Study Day in Table 2 is for the 28-day randomized treatment study phase.
- 13. Targeted physical examination will be conducted on Days 1, 15, 29, and Day 35 (EOS) during the 28-day randomized treatment study phase, please refer to Section 5.2.2.

4.1 **Optional Pre-screening period (Visit 1)**

The Pre-screening visit is optional. Study procedures will be performed according to the Study Plan in Table 1.

At Pre-screening, the consenting patients are assessed to ensure that they meet eligibility criteria for the optional Pre-screening part of the study. Patients who do not meet these criteria must not be entered in the optional Pre-screening part of the study.

- Review and confirm the patient's eligibility for the optional Pre-screening part of the study by assessing inclusion and exclusion criteria listed in Sections 3.1 and 3.2.
- One potassium sample will be assessed using i-STAT.
- If i-STAT potassium value is <5.1 mmol/L the patient will be declared a pre-screen failure and discontinue from the study. There is no limit to the number of pre-screenings a patient can take part in.
- Record SAEs

Note: Patients who meet all optional Pre-screening inclusion/exclusion criteria and i-STAT potassium value is \geq 5.1 mmol/L will be entered into the screening part of the study within 7 days.

